6.9 Reporting urgent safety measures

If any urgent safety measures are taken the Chief Investigator or authorised delegate will immediately and, in any event, no later than 3 days from the date the measures are taken, give written notice to the relevant REC of the measures and the circumstances giving rise to them.

7 STATISTICAL ANALYSES

7.1 Statistical Analysis Plan

We will construct a detailed Statistical Analysis Plan, signed off by the Chief Investigators and Trial Steering Committee prior to the first interim analysis. We will summarise baseline characteristics by randomisation arm within each comparison using appropriate statistical measures (mean, standard deviation; median, interquartile range; frequencies; percentages). The flow of participants through both comparisons will be reported according to the CONSORT Extension for Adaptive Designs (32). We will target a treatment policy estimand to estimate the effect of each intervention as delivered in practice regardless of any events that occur post-randomisation. The efficacy and safety analyses for both randomisations will be based on the intention-to-treat population. Missing data is expected to be very low as this is retrieved from NNRD. It is specified in the Parent Information Leaflet that should they withdraw consent for their baby's participation, data already available in the NNRD will be utilised.

7.2 Sample size and power

7.2.1 Main study

This is a group-sequential trial with 2 interim and 1 final analysis (i.e., an adaptive trial), hence the sample size is not fixed. The maximum sample size is 3252, (n=2168 in each randomisation; n=1084 per arm) assuming no early stopping, estimated on the composite primary efficacy outcome (survival to 34 weeks gestational age without surgical NEC (Y/N)).

Title: COLLABORATE	EDGE No: 181495	Sponsor: Imperial College London	Version: 3.0; 09/01/2026
---------------------------	---------------------------	--	---------------------------------

For the randomisation 1 (pHDM vs Formula supplement) an observational analysis of NNRD data estimated the difference in the proportion surviving to 34w PMA for babies born <29 weeks' gestation to vary between 0.18 and 0.52 depending on week of gestational age (favouring supplementation with preterm formula) (6) For the sample size calculation we targeted a highly conservative MCID in this proportion of 0.05 based on a baseline of 0.82 which we accurately estimated from the NNRD for this population of babies in the UK (i.e. from 0.82 to 0.87).

For randomisation, 2 (fortifier vs no routine fortifier) an unpublished observational analysis from NNRD data estimated the difference in proportion data surviving to 34w PMA for babies born <29 weeks gestation to vary between 0.06 and 0.75 depending on week of gestational age (favouring fortifier). Taking a conservative approach and in line with the first comparison, we have chosen to target the same MCID of 0.05.

We have calculated power based on a fixed sample size of 3252 unique babies using rpact (33) where interim timings were chosen to minimise the expected sample size. We anticipate at least 50% of babies will be co-enrolled into both randomisations. If co-enrolment is higher, power will increase. We have used an O'Brien & Fleming design with two-sided overall significance level of 5% to account for two interims at 50% and 75% and a normal approximation assumption for rates. For both randomisations we have factored in 2% missing outcome data due to carers withdrawing consent from routine data collection in NNRD.

Based on all the above assumptions, n=3252 (n=2168 in each randomisation and n= 1084 per arm) will achieve a minimum of 87% power for each randomisation. The expected sample size across for each randomisation is n=2439.

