This is an adaptive trial; hence the sample size is not fixed. The maximum sample size is 3252, assuming no early stopping and based on the following assumptions: i) Minimum Clinically Important Difference (MCID) of 0.05 (from 0.87 to 0.82) in the proportion "survival to 34 weeks gestation without surgical NEC" (primary outcome); ii) 2- sided alpha of 0.05; iii) 87% power with three planned looks at the data with stopping rules for efficacy (at 50%, 75%, and 100% recruitment); iv) maximum 2% withdrawal rate of consent to use National Neonatal Research Database (NNRD) data; v) 50% co-enrolment rate.

Mechanistic study: 120 infants provide 80% power (2-sided; alpha=0.05) to detect a 10% difference in fractional anisotropy using 3T brain MRI tract-based spatial statistics (measure of white matter microstructure).

INCLUSION/EXCLUSION CRITERIA

Randomisation 1

Inclusion

- Born <29 weeks gestation

Title: COLLABORATE	EDGE No: 181495	Sponsor: Imperial College London	Version: 3.0; 09/01/2026
---------------------------	---------------------------	--	---------------------------------

- No condition precluding enteral feeding
- Maternal intention to express breast milk
- Parent/guardian verbal consent

Exclusion

- Baby has already received pHDM or Preterm Formula

Randomisation 2

Inclusion

- Born <29 weeks gestation
- No condition precluding enteral feeding
- Maternal intention to express breast milk
- Parent/guardian verbal consent

Exclusion

- Baby has already received Fortifier

Mechanistic study Inclusion

- Participants in randomisation 1 recruited at the Royal Infirmary of Edinburgh
- Parent/guardian written consent

Exclusion

- Infants with congenital anomalies: structural or functional (e.g., metabolic disorders) that occur during intrauterine life and can be identified prenatally, at birth or later in life (WHO definition)
- Infants in whom MRI at 3Tesla is contraindicated

INTERVENTIONS and COMPARATORS

Randomisation1

Intervention

- pHDM from a UK human milk bank

Comparator

- Standard commercial Preterm Formula

Randomisation 2

Intervention

- Routine addition of commercial protein-carbohydrate cow-milk derived fortifier to human milk feeds

Comparator

Title: COLLABORATE	EDGE No: 181495	Sponsor: Imperial College London	Version: 3.0; 09/01/2026
---------------------------	---------------------------	--	---------------------------------

- No routine use of fortifier

OUTCOME MEASURES

Primary

Assessed at 34 weeks postmenstrual age

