7.10 Internal pilot

We will run an internal pilot to assess recruitment rate; co- enrolment rate; and withdrawal of consent rate. The internal pilot will run for 9 months (6-15 months).

We need adequate recruitment for each of the comparisons to be powered to detect the MCID of 0.05. We estimate recruitment will increase over the first 9 months from 25 per month to an average of 97 by month 6.

The proportions of babies taking part in both randomisations is important to monitor as this will impact the power of the study. If less than 30% take part in both randomisations, then power will be <80%.

We will also monitor the sample size assumption for missing data which will occur when carers/parents withdraw consent for use of their baby’s information in NNRD to be analysed.

The internal pilot will run seamlessly into the main study if all three criteria below are met.

Progression Criteria	Recruitment per comparison	Proportion taking part in both trials	Withdrawn consent for use of NNRD data
-----------------------------	-----------------------------------	--	---

Title: COLLABORATE	EDGE No: 181495	Sponsor: Imperial College London	Version: 3.0; 09/01/2026
---------------------------	---------------------------	--	---------------------------------

RED: Consider Stopping	<322 randomisations in each comparison	<30% (as trial will have <80% power)	>10%
AMBER: Explore approaches to achieve target	322-644 randomisations in each comparison	30-50%	>2% but < 10%
GREEN: Continue without changes	>644 recruited to each comparison	>50%	<= 2%

The Trial Steering Committee will be responsible for assessing the internal pilot outcomes and provide guidance to the trial team.

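### Protocol section 7.2.1 gives an expected sample size per randomisation (2439) above the stated maximum (2168), and the 50% co-enrolment rate has no stated denominator

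*Protocol*

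**What the plan says.** Section 7.2.1 of the Protocol opens with the maximum: "The maximum sample size is 3252, (n=2168 in each randomisation; n=1084 per arm) assuming no early stopping". It describes the total as "a fixed sample size of 3252 unique babies", so 3252 counts babies and not randomisations. On overlap it says: "We anticipate at least 50% of babies will be co-enrolled into both randomisations". It closes with: "The expected sample size across for each randomisation is n=2439".

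The Trial Summary (Sample size) lists a "50% co-enrolment rate" among the assumptions and does not say what it is a percentage of. Section 7.10 uses the same quantity in the pilot progression table, with red below 30%, amber from 30% to 50% and green above 50%. It adds: "If less than 30% take part in both randomisations, then power will be <80"%. No denominator is given there either.

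The other inputs are a target difference of 0.05 ("i.e. from 0.82 to 0.87"), a two-sided 5% level, an O'Brien-Fleming design with looks at 50%, 75% and 100%, 2% missing outcomes and at least 87% power. Section 7.4 gives critical values of 2.863, 2.337 and 2.024. It also gives numbers at the final look of 1908 for randomisation 1 and 2126 for randomisation 2.

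**The concern.** The expected size of a group-sequential design is an average over the sizes at which it can stop, and none of those exceeds the maximum. A value of 2439 against 2168 therefore cannot be right as labelled. It matters because section 7.2.1 says the interim timings were chosen to make this quantity small. The figure meant to show the benefit of the looks is the one misreported, and as printed it shows no saving.

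The second issue is the meaning of 50%. Section 7.2.1 speaks of babies and counts 3252 unique ones, so the plain reading is half of all babies. The other figures fit only a different denominator. The pilot table turns the same undefined percentage into a continue, explore or consider-stopping signal for the Trial Steering Committee.

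**Working it through.** **Inputs.** From section 7.2.1: 3252 unique babies, 2168 per randomisation, 1084 per arm, rates 0.82 and 0.87, 2% loss. From section 7.4: critical values 2.863, 2.337 and 2.024 at information fractions 0.5, 0.75 and 1.

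**1. Reproducing the design.** Exact two-sided O'Brien-Fleming bounds for these looks are 2.863, 2.337 and 2.024, with overall alpha 0.0500. The critical values reproduce. Power is 88.9–89.0% at 2168, and 88.3–88.4% after 2% loss (2168 × 0.98 ≈ 2125). The stated minimum of 87% is met.

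**2. Expected size at the target difference.**
- Standard error (unpooled) = √[(0.82 × 0.18 + 0.87 × 0.13)/1084] = √(0.2607/1084) = 0.01551.
- Expected Z at full size = 0.05/0.01551 = 3.22.
- Probability of stopping at look 1 is 0.280. Probability of stopping at look 2 is 0.400.
- Expected fraction = 0.5 × 0.280 + 0.75 × 0.400 + 1 × (1 − 0.280 − 0.400) = 0.140 + 0.300 + 0.320 = 0.760.
- Expected size = 0.760 × 2168 ≈ 1648. Pooled variance gives 0.761, or 1650.

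**3. Expected size under no effect.** The stopping probabilities are 0.0042 and 0.0167, so the fraction is 0.994 and the size about 2154. The stated 2439 lies above this and above the ceiling of 2168.

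**4. Where 2439 might come from.** 0.75 × 3252 = 2439. Two origins fit that number.
- A trial-wide expected total. Step 2 scaled to 3252 gives 2472–2475, or 2486–2489 with 2% loss, assuming both randomisations stop at the same fraction. The stated figure is within 3% of these.
- The number enrolled per randomisation if half of all unique babies joined both: (3252 + 1626)/2 = 2439.

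The document does not say which.

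**5. Co-enrolment.** Overlap = 2 × 2168 − 3252 = 1084 babies.
- As a share of each randomisation: 1084/2168 = 50%. Equivalently, 2168 × 1.5 = 3252.
- As a share of all babies: 1084/3252 = 33.3%.

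**6. The pilot table.** A trial exactly on its 3252/2168 design scores 33% (amber, about 3 points above red) on the second denominator and 50% (the amber/green boundary) on the first. The 30% threshold does not reveal which was meant. With 3252 babies split equally between the randomisations:
- 30% of all babies gives 3252 × 1.3/2 ≈ 2114 per randomisation, about 2072 after loss, and power of about 87.5%.
- 30% of each randomisation gives 3252/1.7 ≈ 1913, about 1875 after loss, and power of about 84%.

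Neither is below 80%.

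**7. Dependence on the section 7.4 maxima.** The 2126 for randomisation 2 matches 2168 less 2%, rounded up by arm (1063 × 2). The 1908 for randomisation 1 does not match 2168. With these as maxima the expected sizes at the target difference are about 1625 (2126) and about 1500 (0.788 × 1908).

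**The case against.** The strongest reply is that the design calculation is sound and only a label slipped. The bounds reproduce exactly, the power is met, and the sentence carrying 2439 is visibly garbled, as if an edit had merged a trial-wide statement with a per-randomisation one. No boundary, power figure or recruitment count uses 2439. All of this stands, and it limits the point to the reported expected size.

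A reader might also infer that 3252, 2168 and 50% cannot all be true, and so that the maximum is too large for its purpose or that the power is misstated. The documents do not support that. 2168 × 1.5 is exactly 3252, and an overlap of 1084 is exactly half of each randomisation. A fit that close suggests this denominator was used. The conflict arises only if the 50% is taken over all unique babies. What remains is wording that points to one denominator while the arithmetic uses another.

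It is also fair to say that the pilot's recruitment criterion is a count per comparison and needs no co-enrolment denominator. Only the co-enrolment criterion is exposed.

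**Conclusion.** The expected sample size is wrong as written: 2439 per randomisation cannot stand beside a maximum of 2168. At that maximum the design's own inputs give about 1650 at the target difference and about 2154 under no effect. This rests on the stated rates, looks and critical values and on a normal approximation. The choice of variance formula moves the first figure by about 2.

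The co-enrolment figures are consistent on one denominator (50% of each randomisation) and inconsistent on the literal one (33% of all babies). The fault is the missing definition. Its practical consequence is that the same pilot data could be classed differently by section 7.10. The 87% power and the 3252 maximum need not change.

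**What to change.** 1. Reconcile the per-randomisation maximum in section 7.2.1 (2168) with the final-look numbers in section 7.4 (1908 and 2126). Then rerun the existing sample-size script and replace 2439 with the expected size per randomisation: about 1650 at the target difference if the maximum is 2168. State the effect size it assumes, and preferably give the no-effect value (about 2154) beside it. If 2439 was meant as a total across all babies, label it so and say how the two randomisations were combined.

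2. State the overlap as a count: 1084 babies, which is 50% of each randomisation and 33% of all babies. Use one denominator in the Trial Summary, section 7.2.1 and section 7.10, and recheck the statement linking 30% to power below 80% on that basis.

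The cost is text edits and one script rerun. The co-enrolment definition should be settled before the pilot review applies the thresholds.

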7.2.2 Mechanistic sub-study

Based on computational modelling and prior precedent from neonatal neuroprotection trials, a study of 60 infants in each treatment group will enable detection of a 10% difference in fractional anisotropy with 80% power, 2-sided 5% significance (34).

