3.2 Mechanistic study

3.2.1 Encephalopathy of prematurity

COLLABORATE includes an embedded mechanistic sub-study led by Co-I [name] that will use magnetic resonance imaging (MRI) to determine whether pHDM and Preterm Formula have different effects on cerebral white matter maturation, the hallmark feature of encephalopathy of prematurity, and hence impact the development of brain networks that underpin cognition. We will explore the potential differential effects of the interventions on cortical morphology and microstructure. This sub-study will involve 120 infants participating in COLLABORATE from the Royal Infirmary of Edinburgh. They will undergo 3T brain MRI using a research-dedicated, Wellcome-funded, brain-optimised Siemens MAGNETOM Prisma 3T scanner and 16-channel phased-array paediatric head and neck coil.

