6.8 Adverse reaction reporting

The use of pHDM, Preterm Formula and fortifier are established in routine care. In this extremely preterm population, we anticipate frequent foreseeable AE, SAE and AR, and a mortality rate to discharge from neonatal care of around 10%. For these reasons, AE, SAE, and AR will not be recorded.

All expected SAR have been listed as study endpoints, hence these events will be excluded from safety reporting. Any other SAR will be **unexpected** and extremely rare. These **unexpected** events will be reported to the Sponsor and Ethics Committee within 15 days of the investigator becoming aware of the event.

Cumulative data for safety endpoints (including expected SAR) will be included in regular safety reports reviewed by the Data Monitoring and Ethics Committee in accordance with the charter. Due to the established use of all trial interventions, additional safety oversight of expected events is not required.

Reporting of unexpected SAR will be performed through the eCRF. Unexpected SAR should be reported within 24 hours of the site study team becoming aware of the event as serious, unexpected and related (as described in section 6.4 and 6.6). SAR will be reported to the Sponsor's delegate (ICTU). Further details can be found in the safety reporting manual.

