7.8 Mechanistic sub-study

We will prepare a mechanistic Statistical Analysis Plan prior to any data analyses. We will use Tract-based Spatial Statistics (TBSS) optimised for neonates to compare voxel-wise statistics

Title: COLLABORATE	EDGE No: 181495	Sponsor: Imperial College London	Version: 3.0; 09/01/2026
---------------------------	---------------------------	--	---------------------------------

across the white matter skeleton between treatment groups using a general linear model adjusting for gestational age at birth, age at image acquisition, and any important covariates that remain imbalanced after randomisation (35,36). Significance will be set as $p < 0.05$, following family-wise error rate correction and threshold-free cluster enhancement. TBSS results will be reported as maps overlaying the skeleton where voxels with p -values < 0.05 are highlighted using a colour bar to show the range of significant values.

Participants will be excluded from TBSS analyses if i) there is a parenchymal injury or brain abnormality identified on structural MRI by clinical reviewers considered likely to confound image registration; ii) if there is no diffusion MRI, or excessive motion; iii) if more than 10 diffusion weighted MRI volumes had slice dropout; or iv) if registration fails. Application of these exclusion criteria will be blind to treatment group allocation to reduce the risk of selection bias. Image analysts will be blind to treatment group allocation until analyses are completed.

Diffusion tensor imaging (DTI) data will be analysed using Functional MRI of the Brain Software Library (37) and DTI-ToolKit. Data will be corrected for phase encoding distortions, eddy-induced distortions and motion using the topup-eddy algorithm, using T2 structural volumes rigidly registered to b0 maps and assuming a bandwidth of zero (no phase-encoding) (38). A diffusion tensor model will be fitted to each voxel and the eigenvalues and eigenvectors used to convert the corrected diffusion weighted images into diffusion tensor volumes.

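### The MRI sub-study's 80% power needs 60 analysed infants per group, but 120 is the number taking part and no allowance is stated for the planned TBSS exclusions

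*Protocol*

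**What the plan says.** The sample size statement in section 7.2.2 is that "a study of 60 infants in each treatment group will enable detection of a 10% difference in fractional anisotropy with 80% power", at a two-sided 5% level. The Trial Summary, under sample size, gives the same figure as a total: "120 infants provide 80% power (2-sided; alpha=0.05) to detect a 10% difference in fractional anisotropy".

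Section 3.2.1 describes the people behind that number: "This sub-study will involve 120 infants participating in COLLABORATE from the Royal Infirmary of Edinburgh. They will undergo 3T brain MRI". So 120 is the number taking part and being scanned.

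Section 7.8 lists who leaves the endpoint analysis. It begins "Participants will be excluded from TBSS analyses if" and names four grounds: parenchymal injury or a brain abnormality likely to disturb registration; no diffusion MRI or excessive motion; slice dropout in more than 10 diffusion volumes; and failed registration. No expected rate is given.

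Two other places bear on the point. Section 6.8 expects, for the trial population, "a mortality rate to discharge from neonatal care of around 10" per cent. Section 7.2.1 builds a 2% allowance for missing outcome data into the main trial; section 7.2.2 states none for the sub-study.

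**The concern.** The number that the power statement needs and the number that takes part are the same, 120, with no margin between them. The sub-study's endpoint is fractional anisotropy (FA) by TBSS (section 2.4.3), so an infant excluded from TBSS contributes nothing to the comparison the 80% describes. On the plain reading of section 3.2.1, the stated power therefore belongs to a larger sample than the one that will be analysed.

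This is the only sample size statement for one of the trial's named tertiary objectives (section 2.3). If the MRI comparison shows no difference, readers will set that result against 80% power for a 10% difference. The analysed sample may have less.

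**Working it through.** **Inputs from the protocol.** 60 infants per group, 80% power, two-sided 5%, 10% difference in FA (section 7.2.2). Mortality to discharge about 10% (section 6.8). Scan at 37-44 weeks postmenstrual age (section 5.2.2.2).

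**Inputs not in the protocol.** The mean and standard deviation of FA, and the TBSS exclusion rate. The 80% is attributed to modelling and a cited source, so it cannot be reproduced independently. The loss rates below are assumptions.

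**Step 1: calibrate.** Take a two-sample comparison of means that gives exactly 80% at 60 per group:

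d = (1.960 + 0.842) × √(2/60) = 0.511

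For a 10% difference this implies a standard deviation of 10/0.511 ≈ 19.6% of mean FA. Putting d back in returns 60 per group and 80% by construction; it does not confirm the protocol's figure.

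**Step 2: reduce the analysed number.** Hold d fixed, assume losses balanced between arms, and use

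power = Φ(d × √(n/2) − 1.960), detectable difference at 80% power = 10% × √(60/n)

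| Assumed loss | Analysed (total) | n per group | Power | Detectable difference |
|---|---|---|---|---|
| 0% | 120 | 60 | 80% | 10.0% |
| 5% | 114 | 57 | 78% | 10.3% |
| 10% | 108 | 54 | 76% | 10.5% |
| 15% | 102 | 51 | 73% | 10.8% |
| 20% | 96 | 48 | 71% | 11.2% |

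As an example, at n = 54: 0.511 × √27 = 2.658; 2.658 − 1.960 = 0.698; Φ(0.698) ≈ 0.76. A noncentral-t version (d = 0.516) agrees to within 0.2 percentage points over this range.

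**Step 3: only if 120 is counted at consent.** About 10% mortality alone leaves 108 infants, or about 76% power. If a further 10-20% of the scans were excluded, the fraction analysed would be 0.90 × 0.90 = 0.81 down to 0.90 × 0.80 = 0.72. That is a loss of 19-28% and power of about 71% to 66%.

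**The case against.** The strongest reply is that section 7.2.2 is conditional: it says what a study with 60 per group can detect, not that 60 per group will be consented. If the sponsor means 120 analysable scans, the 80% stands and only a recruitment target is missing. That is fair, and it rules out saying that the power will not be achieved. A reader might infer that; the document does not establish it. But section 3.2.1 attaches the same 120 to infants taking part and being scanned, and nowhere calls it the analysable number.

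A second reply concerns deaths. Section 3.2.1 describes infants who are scanned, and these have survived to the scan. A reader might infer that the 10% mortality must come off the 120. The text does not support that as a certainty, because section 5.2.1.2 leaves the time of approach open. Stool collection from enrolment (section 3.2.2) suggests early entry, but MRI and stool sampling are treated as separable (sections 4.2.3 and 5.8). The deaths therefore count only if 120 is fixed at consent.

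A third reply is that a two-sample test is not the planned analysis, which is voxel-wise, covariate-adjusted and corrected for family-wise error with cluster enhancement. This also stands. The table shows roughly how power falls with the analysed number; it is not a power calculation for TBSS. The cited modelling may also hold some slack at 60 per group that cannot be seen here.

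Finally, section 7.8 promises a mechanistic analysis plan. It is due only before data analysis, however, and the number, the power and the exclusions are already fixed in the protocol.

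**Conclusion.** The point holds as a mismatch within the protocol. The 80% is tied to 60 per group, the same 120 is used for infants taking part and scanned, and planned exclusions from the endpoint analysis carry no stated allowance. If 120 is the number scanned, the stated power is too high by an amount the document does not allow one to fix.

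As an approximation, the shortfall is about 2 percentage points at 5% loss, 4 at 10% and 9 at 20%. This assumes that power is exactly 80% at 60 analysed per group, that losses are balanced, and that a two-sample test is a fair guide to how power scales. A loss of 5% or less would matter little.

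Nothing is miscalculated: 2 × 60 = 120, and the two power statements agree. The endpoint is tertiary, and the primary comparisons are unaffected.

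**What to change.** Keep 120 as the number enrolled or scanned, and say which. In section 7.2.2 and the Trial Summary, state that 80% applies to 60 infants per group with analysable TBSS data. Then give the power, or the difference detectable with 80% power, for the analysable number expected. Use the sponsor's own expected TBSS exclusion rate, plus mortality before the scan if 120 is counted at consent. The figures should come from the sponsor's modelling, not from the approximation above.

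The cost is a sentence or two and a slightly less favourable stated power; no extra infants are needed. Redefining 120 as the analysable number is a different and dearer choice. By 120/(1 − loss), it would mean entering 127 infants at 5% loss, 134 at 10% or 150 at 20%, all from a single site.
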